#### **Planning Target Volume (PTV)**

PTV incorporates a margin that accounts for daily set up variation. The PTV should be a 0.5 cm expansion of all CTVs. Modification of PTV is allowed at the discretion of the treating radiation oncologist for sparing of normal tissues, or if it is needed to facilitate the planning process, e.g. if the PTV overlaps a critical structure that must be spared. Each CTV will have an individual PTV designed for set-up uncertainty.

#### **Avoidance Structures**

The following normal tissue structures will be defined. The dose constraints are listed for each structure.

- A. Spinal cord: Maximum dose  $< 45$  Gy
- B. Expanded spinal cord (5 mm expansion around spinal cord): Maximum dose  $< 50$  Gy
- C. Brainstem: Maximum dose  $< 54$  Gy
- D. Parotid glands: Mean dose  $< 26$  Gy. If this is not possible due to adjacent disease, then the volume of one parotid gland receiving 30 Gy or more (V30) should be  $< 50\%$ .
- E. Larynx: Mean dose  $< 45$  Gy

CONFIDENTIAL

This document is confidential. Do not disclose or use except as authorized.

- F. Mandible: Maximum dose <70 Gy
- G. Oral cavity: Mean dose <45 Gy

For cases in which treatment volumes approach the base of skull, the following avoidance structures will be added:

- A. Inner ear: Mean dose <50 Gy
- B. Optic nerves: Maximum dose <50 Gy
- C. Optic chiasm: Maximum dose <50 Gy
- D. Expanded optic nerve and chiasm (2 mm expansion around these structures): Maximum dose <54 Gy
- E. Retina: Maximum dose <45 Gy
- F. Brain: Maximum dose <60 Gy

### **Target Dose Prescriptions**

To accommodate for tissue heterogeneity, density corrections are required, and will be applied to all plans, unless contraindicated, for example, by significant amounts of scatter on the planning CT scan.

#### **Group II and Group IIIA**

- **PTV50 will be treated to a total dose of 50 Gy in 2.0 Gy/fraction.**

#### **Group IIIB**

- **PTV56 will be treated to a total dose of 56 Gy in 2.0 Gy/fraction.**
- **PTV50.4 will be treated to a total dose of 50.4 in 1.8 Gy/fraction.**
- **PTV56 and PTV50.4 will be treated via simultaneous integrated boost (SIB) technique.**

#### **PTV Coverage**

All plans must be normalized such that 95% of the PTV is covered with the prescription dose. No more than 20% of the PTV may receive > 110 % of the prescription dose. No more than 1% of the PTV may receive < 93% of the prescription dose. No more than 1cc of tissue outside the PTV may receive > 110% of the prescription dose.

**Note:** in any case with a conflict/overlap between target and normal tissue, target dose considerations will take priority, with the exception of the spinal cord limits.

#### **Treatment Breaks**

There are no planned treatment breaks on this study; any breaks in planned radiotherapy are strongly discouraged. Radiotherapy interruptions will be permitted for unavoidable mechanical malfunction or serious illness requiring hospitalization, such as sepsis, delirium, severe respiratory compromise or hemodynamic instability, at the discretion of the Principal Investigator. Treatment breaks should be as short as possible. The reason for any interruption in treatment must be documented in the treatment chart.

#### **Quality Assurance**

**Initial:** Prior to the first radiation treatment, the standard quality assurance procedures will be followed. The monitor units required to deliver the prescribed dose shall be calculated. The monitor units generated by the IMRT planning system must be independently checked prior to the patient's first treatment. Measurements in

**CONFIDENTIAL**

This document is confidential. Do not disclose or use except as authorized.

a quality assurance phantom will be done for each patient that will be treated. An ion chamber measurement, to assess absolute dose, in addition to a film or matrix measurement will be taken during the QA period.

On the first day of treatment each patient will have electronic portal images taken that localize the isocenter placement, which will be approved by a radiation oncologist prior to delivery of the first treatment, per standard practice.

**Weekly:** Verification portal images will be taken at least once per week and approved by a radiation oncologist prior to continuation of treatment per standard practice.

### **Isodose Distribution**

All plans will have complete documentation in the patient's chart, including representative CT slices with treatment isodoses. A DVH with all PTV and CTV structures and all normal tissue structures will be generated for each patient and documented in the patient's radiotherapy chart.

### **Quality Assurance:**

Each treatment plan will be reviewed by at least one non-treating radiation oncologist prior to therapy to assure that the appropriate fields and doses will be delivered.

## **Chemoradiotherapy Treatment Plan**

### **5.1 Chemoradiotherapy**

#### Chemoradiotherapy Agent Administration

##### Cisplatin

Dose: 40mg/m^2/week

Route: IV over approximately 30 minutes, mixed in 250ml normal saline

Schedule: Weekly on Monday or Tuesday any time, or Wednesday prior to radiation

Prehydration: Prehydration IV fluids are required, KCl and Magnesium sulfate will be administered as well as antiemetic regimen to include a 5HT3 antagonist prior to cisplatin administration.

All patients assigned to Group IIIA and Group IIIB will receive daily radiation treatment with intensity-modulated radiotherapy (IMRT). Treatment will be given 5 days per week and, as per standard practice, will not be delivered on Saturday, Sunday or major holidays. Radiotherapy will be administered according to the guidelines above.

### **5.2 Salvage Protocol**

In the event of suspected disease recurrence in the surveillance group (Group I), appropriate imaging including PET/CT scan and biopsies will be performed. Biopsies will be evaluated for HPV16 and p16 expression and

CONFIDENTIAL

This document is confidential. Do not disclose or use except as authorized.

stored for further analysis. If there is solely a local regional recurrence, Surgical salvage will be offered to patients who have resectable limited disease defined as recurrent disease at the primary site or level 2 or 3 lymph nodes and <3 positive nodes on scan, followed by post-operative CRT as above for group 3 patients. For patients with limited recurrence deemed unresectable for reasons of organ preservation or ability to reasonably expect a complete surgical resection, definitive CRT with a total dose of 6600-7200 cgy and cisplatin as above will be performed.

For patients with extensive local regional disease defined as infiltrative, >2 positive nodes, nodal involvement of levels 4, 5 or N2c disease or those with metastatic disease, TPF chemotherapy will be given. After completion of 3 cycles of TPF, sites of initial disease will be treated with carboplatin to 5600 cGy as defined in the Quarterback trial. TPF will be given even if the metastases have been completely resected post TPF. CRT will be delivered to sites and watershed areas of metastatic disease that has been resected or is unresectable and there was no LR recurrence. For multiple metastases TPF and CRT may be withheld if in the opinion of the clinician the DM are too numerous and desminated to be safely or effectively treated.

Patients in Group II or Group III who fail with LR disease will be treated with best available therapy.

If a specific and highly effective therapy is identified during the conduct of the study that is an improvement over treatment with TPF and CRT as salvage, that therapy may be offered to the patients as a standard treatment, and will be added as an amendment in due course.

## **6.0 STUDY PARTICIPATION**

### **6.1 Duration of Follow Up**

Participants will be followed for 5 years after completion of study treatment or until death, whichever occurs first through standard of care treatment after therapy as prescribed by the Investigator which can include clinic visits or other follow-up by other means. Participants removed from study for unacceptable adverse events will also be followed until resolution or stabilization of the adverse event.

### **6.2 Criteria for Removal from Study**

Participants will be removed from study when any of the criteria listed below applies. The reason for study removal and the date the participant was removed must be documented in the study-specific case report form (CRF). Alternative care options will be discussed with the participant.

In the event of unusual or life-threatening complications, participating investigators must immediately notify the Principal Investigator, [name] at [contact]

- Patient is removed early from protocol therapy at PI's discretion
- Patient is found ineligible
- Patient completion of protocol requirements
- Unacceptable toxicity
- Pregnancy
- Adverse Event
- Progressive disease/ relapse
- Lost to follow-up (documented 3 attempts via telephone or signature confirmation letter)

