## **1.0 INTRODUCTION**

### **Study Design**

Non-randomized Phase II de-escalation clinical trial to establish recurrence rates, site of recurrence, survival and quality of life outcomes for early T-stage HPV positive oropharyngeal SCCA treated with upfront surgery and reduced dose radiotherapy. Eligible, consented and registered patients will undergo transoral robotic surgery and selective neck dissection. After pathologic evaluation, patients with early stage disease as defined below will be placed into surveillance protocol as outlined or assigned to adjuvant therapy, depending on risk factors. Patients with intermediate risk factors will receive postoperative radiotherapy alone (5000 cGy). Patients with poor prognostic features will receive concurrent chemoradiotherapy (5600 cGy) with weekly cisplatin. Patients taken off study (based on Section 9.2 “Criteria from Removal of Study”) will be followed for survival until the study ends. Any adverse events occurring thereafter in these patients will not be considered related to the study and will not be tracked or reported.

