## **4.0 REGISTRATION PROCEDURES**

After the patient signs the informed consent the patient will be registered for screening and once the investigator has verified that the patient meets all inclusion/exclusion criteria, the patient will be registered for and started on the protocol. Patients who lack p16 and HPV PCR may proceed to surgery however they will not be assigned to an experimental group and registered on the protocol until p16 IHC and HPV PCR are completed and positive. The verification of patient's eligibility and screening completion will be performed centrally after the receipt of the patient primary post-surgical registration form. It is mandatory not to exceed 21 days between the date of registration for screening and the start of the study treatment (surgery). In any case, all events occurring after the registration for therapy must be recorded in the case report form and will be taken into account in the analysis, whether the patient received the study treatment or not. Patient must receive surgery and be p16 IHC and HPV PCR positive to be included in the intent to treat analysis. Patients found to not meet entry criteria will be offered best therapy.

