**CONFIDENTIAL**

This document is confidential. Do not disclose or use except as authorized.

- Non-Compliance with therapy and protocol procedures
- Death
- Other

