## 11.0 MEASUREMENT OF EFFECT

### 11.1.1 Definitions

Evaluable for toxicity. All participants who go on to surgery will be evaluable for toxicity from the time of their first treatment. Patients who are screened will be evaluated and the reason for screen failure will be recorded

Evaluable for Primary Outcome: Only patients who are entered and have surgery will be eligible for assessment of the primary outcomes (LRC, PFS). All patients who have had surgery will be analyzed on an ITT for LRC, PFS, and survival.

Progression-Free Survival: Progression-Free Survival (PFS) is defined as the duration of time from start of treatment to time of objective disease progression or death.

Local Regional Control (LRC) will be defined as local and regional control of disease, censored for death.

Overall Survival (OAS) will be defined as alive at the time of analysis, this will be analyzed as for the entire trial, for all randomized patients and only for those patients randomized who received one dose of radiotherapy.

Post Recurrence LRC: Surveillance Patients who recur will be assessed for LRC post treatment for their initial recurrence

Post Recurrence PFS Surveillance Patients who recur will be assessed for PFS post treatment for their initial recurrence

Ultimate Disease Control will be defined as those patients who are alive and disease free at the time of analysis

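### Stopping protocol treatment triggers removal from study with survival-only follow-up named afterwards, which contradicts the promised ITT analysis of LRC and PFS and leaves no censoring rule

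*Combined protocol and SAP*

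**What the plan says.** Section 6.2 is worded as mandatory: "Participants will be removed from study when any of the criteria listed below applies". Four of its criteria concern treatment or adherence, not the end of observation:

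- "Patient is removed early from protocol therapy at PI's discretion"
- "Unacceptable toxicity"
- "Adverse Event", with no grade or relatedness attached
- "Non-Compliance with therapy and protocol procedures"

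The Study Design paragraph of Section 1.0 says that patients taken off study "will be followed for survival until the study ends", and that their later adverse events will not be tracked. It points to Section 9.2 for the removal criteria. Section 9.2 covers laboratory studies, and the title it gives matches Section 6.2.

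Other sections point the other way. Section 11.1.1: "All patients who have had surgery will be analyzed on an ITT for LRC, PFS, and survival". Section 4.0 requires all events after registration for therapy to be entered in the case report form, and says that they "will be taken into account in the analysis, whether the patient received the study treatment or not". It makes surgery and p16/HPV positivity, not completion of therapy, the conditions for the ITT set. Section 6.1 has participants followed for 5 years after study treatment, through standard-of-care visits or other means.

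**The concern.** A Group II or III patient who stops adjuvant treatment for toxicity, or does not comply with it, is usually free of relapse on that day. Section 6.2 takes the patient off study, and Section 1.0 then names survival as the only thing to be followed. A site acting on those two texts in good faith would have no instruction to report a later local, regional or distant recurrence.

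The two disease endpoints would suffer differently. Section 11.1.1 censors LRC at death, so LRC would lose every locoregional failure after removal. PFS counts progression or death, so it would lose progressions in survivors and date the others late, at death. Both are primary objectives for the de-intensified adjuvant groups (1.1.4 and 1.1.5), and Section 16.1 sets a benchmark above 85% for them. Patients who stop or decline adjuvant treatment may well recur more often than those who complete it. If so, the error favours de-escalation.

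**Working it through.** **Texts side by side, for an operated, p16/HPV-positive, relapse-free patient who stops treatment**

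| Question | Section | Answer |
|---|---|---|
| Does the patient leave the study? | 6.2 | Yes, mandatory |
| What is followed afterwards? | 1.0, Study Design | Survival; adverse events expressly not tracked |
| How long are participants followed? | 6.1 | 5 years; those removed for unacceptable adverse events are also followed until that event settles |
| Are later events recorded? | 4.0 | Yes, all events after registration for therapy |
| Is the patient in the LRC and PFS analysis? | 11.1.1, 4.0 | Yes, by ITT |
| How is the patient censored? | 16.4, 16.5 | Not stated |
| Is off-treatment distinct from off-study on the form? | 14.1 | No, one combined form |

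The second row cannot be squared with the fourth and fifth, and no section ranks them.

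**Size, as an illustration.** The plan gives no figure to reproduce: no removal rate, no recurrence rate after removal, no dropout allowance. Assumptions: 12% locoregional failure in completers; a share f of 5%, 10% or 20% removed relapse-free; a hazard ratio (HR) of 1, 2 or 3 for the removed patients.

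True failure = (1 − f) × 0.12 + f × (1 − 0.88^HR), where 1 − 0.88^HR is 0.120, 0.2256 and 0.3185 for HR 1, 2 and 3. Kaplan-Meier with censoring at removal estimates 12.0% throughout, that is, LRC 88.0%.

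| f | HR | True failure | True LRC | Overstatement (points) |
|---|---|---|---|---|
| any | 1 | 12.0% | 88.0% | 0 |
| 5% | 2 | 0.1140 + 0.0113 = 12.5% | 87.5% | 0.5 |
| 5% | 3 | 0.1140 + 0.0159 = 13.0% | 87.0% | 1.0 |
| 10% | 2 | 0.1080 + 0.0226 = 13.1% | 86.9% | 1.1 |
| 10% | 3 | 0.1080 + 0.0319 = 14.0% | 86.0% | 2.0 |
| 20% | 2 | 0.0960 + 0.0451 = 14.1% | 85.9% | 2.1 |
| 20% | 3 | 0.0960 + 0.0637 = 16.0% | 84.0% | 4.0 |

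**Check on timing.** The table applies the hazard ratio from time zero. If it starts at removal, taken as 6 months on a 3-year horizon, with base failure r:

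true failure = 1 − (1 − r)^(1/6) × [(1 − f)(1 − r)^(5/6) + f(1 − r)^(5·HR/6)].

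For r = 12%, f = 20%, HR = 3: 1 − 0.9789 × (0.8 × 0.8990 + 0.2 × 0.7265) = 1 − 0.9789 × 0.8645 = 15.4%. The overstatement is 3.4 points and true LRC is 84.6%.

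With the same f and HR, the overstatement is 2.9 points for r = 10% and 5.0 points for r = 20%. In a middle case (r = 20%, f = 10%, HR = 2), about 3.0 recurrences per 100 patients go unseen, and 20.0% is estimated against a true 21.4%. At HR 1 the censoring bias is zero in both models.

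**The case against.** A reader might infer that recurrences after removal will not be collected and that the ITT analysis cannot be delivered. The documents do not support either statement.

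- Section 4.0 imposes a duty to record all events, and Section 6.1 gives 5 years of follow-up. Section 1.0 expressly ends only adverse-event tracking.
- Kaplan-Meier estimates can be produced with censoring at removal. They are biased only if removal is informative. Deaths are still captured.
- Section 4.1 has a separate status for patients registered but not treated. Section 7.2 has carboplatin stopped for the rest of therapy without treating that as leaving the study.
- Section 6.1 speaks of unacceptable adverse events, so reading the bare criterion in 6.2 as any event at all is strained.
- Relapse is itself a removal criterion. If removal really ended disease follow-up, objectives 1.1.7 and 1.1.8 and the post-recurrence endpoints of Section 11.1.1 could not be met. That suggests loose drafting.

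All of this stands, and it changes the point from a certain loss of data to a contradiction that puts data at risk. It does not remove it. Section 6.1 is general, and its one sentence on removed participants concerns resolution of the adverse event, not recurrence. Section 1.0 addresses every patient taken off study. The registered-not-treated status says nothing about follow-up.

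Two further readings go too far. Counting removed patients as event-free would raise the extreme case to 16.0% − 9.6% = 6.4 points, but no section prescribes that. And Group I has no adjuvant therapy to stop. Its patients can leave through the adverse event, non-compliance or open-ended criteria, but the effect is mainly in Groups II and III.

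**Conclusion.** The concern holds as an unreconciled contradiction. Sections 6.2 and 1.0 together move a relapse-free patient who stops treatment to survival-only follow-up. Sections 4.0, 6.1 and 11.1.1 require that patient's recurrences to be followed, recorded and analysed. Which text a site applies decides whether LRC and PFS in Groups II and III are complete.

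The size rests wholly on assumptions. With 12% failure in completers, 5-20% removed and HR 1-3, LRC is overstated by 0 to about 4 points under censoring at removal. The conclusion against the 85% benchmark changes only in the most extreme cell. A higher base failure rate gives a larger bias. The direction is upward only if removed patients recur more often, which is plausible but not shown. The matter should still be settled now, because recurrence dates not collected prospectively may not be recoverable.

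**What to change.** Reconcile Sections 1.0 (Study Design), 4.0, 6.1 and 6.2:

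1. Separate discontinuation of protocol treatment from withdrawal from study, and split the combined off-treatment/off-study form in Section 14.1 to match.
2. State that operated, p16/HPV-positive patients who stop treatment stay in their assigned group. Record their recurrence status and any off-protocol treatment through the standard-of-care follow-up of Section 6.1 to 5 years, unless they withdraw consent for follow-up or are lost.
3. In Section 1.0, limit survival-only follow-up to patients who decline further visits, and correct the cross-reference to the removal criteria.
4. In Section 16.4, state how LRC and PFS are censored for patients who leave the study. Add a sensitivity analysis that varies the recurrence rate after exit.

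These changes concern data collection and analysis only. When to stop treatment, and clinical management and imaging afterwards, including in pregnancy, stay with the investigator.

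The cost is a wording amendment, a form change and continued data entry for patients who stopped treatment. The visits are already planned as standard of care, and the Group I sample size of 100 is unaffected.

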**CONFIDENTIAL**

This document is confidential. Do not disclose or use except as authorized.

- Non-Compliance with therapy and protocol procedures
- Death
- Other

## 7.0 EXPECTED TOXICITIES AND DOSING DELAYS/DOSE MODIFICATIONS

### 7.1 Anticipated Toxicities

A list of the adverse events and potential risks associated with the agents administered in this study appear below and will determine whether dose delays and modifications will be made or whether the event requires expedited reporting in addition to routine reporting.

#### 7.1.1 Adverse Event List(s) for Cisplatin

The major dose limiting toxicities observed with Cisplatin single agent are nausea and vomiting, peripheral neuropathy, nephrotoxicity and ototoxicity.

#### 7.1.2 Adverse Event List(s) for Carboplatin

The major dose limiting toxicities observed with Carboplatin single agent are myelosuppression and renal toxicity.

### 7.2 Dose Modifications/Delays

#### 7.2.1 Cisplatin

##### Peripheral Neuropathy

- A neurological examination must be performed at least before entry into the study and then **Should be done at the end of CRT for chemoRT groups and then at 3 month follow up.** In case of symptoms or signs experienced by the patient, more frequent examinations should be performed and dose modification will be as follows:
  - Grade 0, 1: No change
  - Grade  $\geq 2$ : Carboplatin at an AUC of 2 may be substituted for Cisplatin

##### Ototoxicity

- Cisplatin is known to cause high frequency hearing loss. If grade 1 or 2 hearing loss occurs, the risk of additional hearing loss versus the potential benefit of continuing Cisplatin chemotherapy should be made. Grade 3 and 4 hearing loss is an indication to discontinue the drug however this decision can be made with the patient and after formal hearing tests.
- Audiometric testing will be performed at baseline and prior to each dose

CONFIDENTIAL

This document is confidential. Do not disclose or use except as authorized.

- In case of grade 3 or 4 toxicity, Carboplatin (at dosage of AUC 2) may be used to replace Cisplatin in the remaining chemo cycles. The dose of Carboplatin AUC 2 will be calculated based on the Calvert formula.

